- Free of orthopedic limitations that would limit exercise ability
- Be neither a "morning lark" nor a "night owl"

Benefits:

- Body composition testing
- Cardiorespiratory fitness testing (VO_{2max})

For more information, please contact:

[name]
[contact]
[contact]

The University of Montana IRB
Expiration Date 6-15-2022
Date Approved 6-16-2021
Chair/Admin [name]

NCT04955431

October 2, 2024

IRB #83-21 "The Effects of Circadian Rhythm Disruption on the Inflammatory Response to Particulate Matter Exposure from Woodsmoke"

Statistical Power

Utilizing data from Abedelmalek et al. (2012), which found an increase in exercise-induced IL-6 in the blood following acute sleep deprivation, we calculated, using a moderate effect size of 0.4 with an alpha = 0.05 and power = 0.8 that a total sample size of 12 would be sufficient.

Statistical Analysis

We will collect physiological data from participants at baseline (PRE) and immediately after (POST) a simulated wildland firefighting exercise bout on two separate visits to the laboratory. One visit will occur after a night of normal sleep (NS) while the other visit will occur after a night of restricted sleep (RS).

We will perform a 2-way Repeated Measures ANOVA to assess the interaction between exercise and sleep. We will additionally test for simple main effects of exercise (PRE vs POST) and sleep (NS vs RS).

Our experimental hypothesis is that sleep restricted will increase the inflammatory response to simulated wildland firefighting exercise.

Our null hypothesis is that there is not difference between NS and RS in the response to simulated wildland firefighting.

Significance will be accepted at $p < 0.05$.

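### Does a title naming woodsmoke particulate matter and circadian disruption call for a change, when the analysis has only sleep and PRE/POST as factors?

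*SAP*

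**What the plan says.** The SAP title is "The Effects of Circadian Rhythm Disruption on the Inflammatory Response to Particulate Matter Exposure from Woodsmoke". Woodsmoke and particulate matter are not mentioned again in the SAP.

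Under Statistical Analysis, data are collected "at baseline (PRE) and immediately after (POST) a simulated wildland firefighting exercise bout on two separate visits to the laboratory". The visits are distinguished by the preceding night: "One visit will occur after a night of normal sleep (NS) while the other visit will occur after a night of restricted sleep (RS". The model is given as "We will perform a 2-way Repeated Measures ANOVA to assess the interaction between exercise and sleep", followed by "We will additionally test for simple main effects of exercise (PRE vs POST) and sleep (NS vs RS".

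The experimental hypothesis is that "sleep restricted will increase the inflammatory response to simulated wildland firefighting exercise". The null is that "there is not difference between NS and RS in the response to simulated wildland firefighting".

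The Statistical Power section rests on a published finding about exercise-induced IL-6 after sleep loss. The Protocol text available is a fragment of a recruitment notice. It does not describe the bout, the air breathed during it, or the timing of visits.

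**The concern.** The title names an exposure (woodsmoke particulates) and a modifier (circadian disruption). The analysis contains neither under those names. If smoke is part of each bout, PRE versus POST combines exercise, smoke and elapsed time, while the SAP calls that contrast the effect of exercise. If smoke is not part of the bout, the title names something that was not studied. The manipulation is also one night of shortened sleep, which is not the same construct as circadian disruption.

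The stake is attribution. A significant result reported under this title could be read as evidence about particulate matter or circadian rhythm, and the design isolates neither. A larger sample would not cure that.

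**Working it through.** **The plan's own figure.** The SAP gives a total of 12 for effect size 0.4, alpha 0.05 and power 0.80. It does not state the effect metric, the number of measurements m or the correlation rho. Assume that 0.4 is Cohen's f and that sphericity holds, with noncentrality lambda = f² × n × m / (1 − rho) and degrees of freedom (m − 1) and (n − 1)(m − 1):

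- m = 3, rho = 0.5, n = 12: lambda = 0.16 × 12 × 3 / 0.5 = 11.52, power 0.816.
- m = 2, rho = 0.6, n = 12: lambda = 0.16 × 12 × 2 / 0.4 = 9.6, power 0.805.
- m = 4, rho = 0.5: the smallest n is 10, and power at 12 is 0.887.

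So 12 can be reached under common assumptions. It has no bearing on attribution, which does not depend on n.

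**Can a particulate effect be estimated?** Each participant contributes four cells, 2 sleep conditions × 2 times. The model with intercept, sleep, PRE/POST and their interaction has 4 columns and rank 4. Add a particulate term and a particulate-by-sleep term:

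| Case | Particulate column | Columns | Rank |
|---|---|---|---|
| Smoke in both bouts | identical to POST | 6 | 4 |
| No smoke in either | all zeros | 6 | 4 |
| For comparison: smoke/no-smoke factor added (2 × 2 × 2) | varies independently | 8 | 8 |

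The answer is no. Only a design with a no-smoke comparator would separate the particulate part.

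**Does that affect the hypothesised contrast?** Take additive contributions e (exercise), s (smoke, if any) and t (elapsed time). Let r be the sleep shift already present at PRE, and d the extra change across the bout caused by restricted sleep.

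| | PRE | POST |
|---|---|---|
| Normal sleep | a | a + e + s + t |
| Restricted sleep | a + r | a + r + e + s + t + d |

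- PRE to POST under normal sleep: e + s + t. The three parts cannot be separated.
- Interaction: (e + s + t + d) − (e + s + t) = d.

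The aliasing lies in the PRE/POST contrast, which the SAP lists as additional. Whatever is common to both bouts drops out of the interaction. The quantity d is the effect of restricted sleep on the response to the whole bout. It may act through the exercise part, the smoke part or both, and the data cannot divide it.

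**Setting d against the text.** The null hypothesis compares the two sleep conditions on the response to simulated firefighting, which is d = 0. The experimental hypothesis is that restricted sleep makes the inflammatory response larger, which is d > 0. Neither proposes a value for s, nor for the part of d that runs through s.

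**The case for a change.** The strongest case for a change is that wording costs nothing. Title and analysis do not match. The label for PRE/POST is too narrow if smoke was present. Readers concerned with firefighters' smoke exposure could be misled. A restated estimand, a renamed factor and an aligned reporting title need no new visits or participants, and could be done even after data collection.

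Three parts of this stand. A separate particulate effect is not estimable. PRE versus POST should not be credited to exercise alone. The title is broader than the hypotheses.

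The rest is weaker. The restated estimand is largely in the SAP already, because both hypotheses refer to the response to the simulated work and not to particulates. The exercise label is defined where it is used, as PRE versus POST, so a reader can see which contrast is meant. The circadian wording is loose, but the analysis text speaks of sleep throughout, and the recruitment notice screens out both extreme chronotypes. Misattribution is a prediction about a future report, and the SAP commits to no such conclusion. A rule forbidding any statement about particulates is itself open to debate: if smoke was given in both bouts, d concerns the response to a stimulus that includes it, which is close to the effect-modification question in the title. The alternative, that particulate matter was not studied at all, cannot be judged from the text supplied.

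**Conclusion.** No change to the plan is needed. The mismatch is real, but it is one of title and label. The hypothesised test is the sleep by PRE/POST interaction, and it addresses the question that the SAP's hypotheses ask. Renaming a factor, restating an estimand that is mostly written already and editing a title would alter no data, no model term, no p-value and no decision on that hypothesis.

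The limit on interpretation is that the particulate share of the response, and the particulate share of any sleep effect, cannot be estimated at any sample size (rank 4 of 6 columns). The PRE/POST effect is the change across the bout as a whole. An analyst can see this from the stated factors and report accordingly.

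This rests on two assumptions that the supplied text does not settle: that the two bouts were alike in exercise, air and timing, so that their common parts cancel; and that conclusions will follow the stated hypotheses and not the title.

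### Does the claim of 80% power at N = 12 for an effect size of 0.4 fail because the metric, contrast and correlation are not given?

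*SAP*

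**What the plan says.** The SAP, Statistical Power, cites a study of exercise-induced IL-6 after acute sleep deprivation and reports having calculated "using a moderate effect size of 0.4 with an alpha = 0.05 and power = 0.8 that a total sample size of 12" is enough. It states no effect-size metric, mean difference, SD, correlation or powered contrast. The protocol text available is recruitment material and adds nothing on power.

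The SAP, Statistical Analysis, is clearer about the test. Each person is measured before and after exercise at two visits, one after normal sleep (NS) and one after restricted sleep (RS). The plan reads: "We will perform a 2-way Repeated Measures ANOVA to assess the interaction between exercise and sleep". The hypothesis matches that term: "Our experimental hypothesis is that sleep restricted will increase the inflammatory response to simulated wildland firefighting exercise". The null is the corresponding absence of an NS–RS difference in response, and the significance level of 0.05 agrees with the alpha in the power sentence.

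**The concern.** An effect size of 0.4 has several standard meanings, and power at 12 people differs greatly between them. A reader who takes 0.4 as a standardised within-person difference, a natural reading for a design in which everyone is their own control, finds 24% power where the SAP states 80%. If that were the calculation, the trial would have about a one-in-four chance of detecting the effect it was sized for, and a non-significant interaction would say little.

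The word moderate adds to the worry. At 12 people, 80% power for a one-degree-of-freedom within-person test requires a contrast of 0.89 of its own SD, and a reader may not connect that with a moderate 0.4. The SAP gives p < 0.05 as its criterion and mentions no confidence interval, so a null result might be read as showing no effect of sleep restriction.

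**Working it through.** **Inputs.** From the SAP, Statistical Power: effect size 0.4, alpha 0.05, power 0.80, N = 12. From the SAP, Statistical Analysis: a 2×2 fully within-person design and a test of the exercise-by-sleep interaction. The correlation ρ between single measurements on one person is not given. The values below are assumptions, taken as common to all four cells with equal variances.

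**The test.** For each person let D = (POST − PRE under RS) − (POST − PRE under NS). The interaction F test has 1 and N − 1 degrees of freedom and equals a two-sided one-sample t-test of mean D = 0. With dz = mean(D)/SD(D), power is the upper tail of a noncentral F with noncentrality λ = N·dz².

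**Can 12 be reproduced?** Not uniquely, because the inputs do not fix one calculation. The main readings are these.

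1. *0.4 as dz.* λ = 12 × 0.4² = 1.92, power 24.5%. Reaching 80% takes N = 52. This reading does not give 12.

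2. *0.4 as Cohen's f for the interaction on four cell means.* Cell effects of ±0.4 SD give a mean D of 4 × 0.4 = 1.6 single-measurement SDs. Under a common correlation SD(D) = 2√(1 − ρ), so dz = 0.8/√(1 − ρ).

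| ρ (assumed) | dz | λ = 12·dz² | Power at 12 | N for 80% |
|---|---|---|---|---|
| 0 | 0.800 | 7.68 | 71.4% | 15 |
| 0.2 | 0.894 | 9.60 | 80.5% | 12 |
| 0.3 | 0.956 | 10.97 | 85.4% | 11 |
| 0.5 | 1.131 | 15.36 | 94.5% | 9 |
| 0.6 | 1.265 | 19.20 | 97.8% | 8 |

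Power reaches 80% at 12 people from ρ of about 0.19.

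3. *0.4 as f in a generic repeated-measures calculation with m measurements,* λ = f²·N·m/(1 − ρ), on m − 1 and (N − 1)(m − 1) degrees of freedom:
   - m = 2, ρ = 0.6: λ = 0.16 × 12 × 2/0.4 = 9.60, power 80.5%, N = 12.
   - m = 3, ρ = 0.5: λ = 0.16 × 12 × 3/0.5 = 11.52, power 81.6%, N = 12.
   - m = 4, ρ = 0.4: λ = 0.16 × 12 × 4/0.6 = 12.80, power 81.8%, N = 12.

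   These are not the interaction. With m = 2 the comparison is between two cells, for example PRE against POST. Under a common correlation the two visits' change scores are themselves uncorrelated (ρ − ρ − ρ + ρ = 0), so ρ = 0.6 cannot be carried over to them. With m = 4 the test has 3 degrees of freedom. They show only that 12 is what routine inputs return.

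4. *0.4 single-measurement SDs as the raw difference in change.* dz = 0.4/(2√(1 − ρ)), which is 0.200 at ρ = 0 and 0.283 at ρ = 0.5. Power is about 10% and 15%. This reading does not give 12 either.

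**A figure that needs neither metric nor correlation.** Solving for 80% power at N = 12 gives dz = 0.889. With 10 completers it is 0.996. In single-measurement SDs, 0.889 × 2√(1 − ρ) is 1.78, 1.26, 0.79 and 0.56 at ρ = 0, 0.5, 0.8 and 0.9.

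**Precision.** The 95% interval for mean D has half-width t(0.975; 11)/√12 = 2.201/3.464 = 0.635 SD of D.

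**The case for a change.** The strongest case for acting is that the sentence cannot be checked. It returns 12 only after a metric and a correlation are supplied from outside, and under two plausible readings power is 24% or less. A line stating the detectable contrast as 0.89 of its own SD would cost nothing, use no outcome data and be right under every reading. An interval would also guard against overreading a null result: with 12 people, even an observed difference of zero leaves values up to 0.64 SD in either direction open.

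Most of this stands as a comment on reporting. The omission is real, and the 0.89 and 0.64 figures are correct. It does not establish an error. Readings that fail to return 12 are poor evidence about what was calculated when other standard ones do return it. The spread of power across readings depends on which correlations one tabulates, so no particular range can be attributed to the SAP.

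Nor does the 0.89 figure contradict a moderate 0.4. Any one-degree-of-freedom within-person test with 80% power at 12 people has dz = 0.889, so if f was meant, the two numbers describe the same effect on different scales. As for null results, the SAP nowhere says that a non-significant interaction will be taken as proof of no difference. Its null, "Our null hypothesis is that there is not difference between NS and RS in the response to simulated wildland firefighting", is the ordinary statement of what is tested.

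**Conclusion.** No change to the plan is needed. The power sentence lacks detail: its metric, contrast and correlation are unstated, so the calculation cannot be uniquely reproduced. It fits Cohen's f = 0.4 with a correlation of about 0.2 for the interaction on four cell means, or 0.4 to 0.6 in generic repeated-measures calculations. It does not fit a standardised within-person difference of 0.4, which would have 24% power and need 52 people. Nothing in the documents says that the latter was meant.

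Stating the missing inputs would leave the sample at 12 and the interaction test, its validity and its p-value unchanged. An analyst running the planned model can also report the RS-minus-NS difference in change with its interval as routine output.

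A colleague interpreting the result should work with a detectable contrast of 0.89 of its own SD. This assumes a two-sided test, as the ANOVA F test implies, and 12 completers, since the SAP states no dropout allowance. The power figures for f also assume equal variances and a common correlation. Whether 12 is adequate for the effect in the cited study cannot be judged, because its means, SDs and correlations are not given.

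### The exercise-by-sleep ANOVA names no visit-by-exercise (sequence) term; adding one is a low-cost improvement, provided both visit orders were used

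*SAP*

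**What the plan says.** Under Statistical Analysis, the SAP has measurements before and "immediately after (POST) a simulated wildland firefighting exercise bout on two separate visits to the laboratory", with one visit following each sleep condition. The hypothesis is directional: "Our experimental hypothesis is that sleep restricted will increase the inflammatory response to simulated wildland firefighting exercise". The null is worded as "Our null hypothesis is that there is not difference between NS and RS in the response to simulated wildland firefighting".

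The one model named is in this sentence: "We will perform a 2-way Repeated Measures ANOVA to assess the interaction between exercise and sleep". The follow-up tests are for exercise and for sleep, and the SAP calls them simple main effects. No visit, period, order or sequence factor is named.

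Under Statistical Power, the sample size of 12 is obtained "using a moderate effect size of 0.4 with an alpha = 0.05 and power = 0.8".

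The readable text does not say which sleep condition came first, how order was assigned, or how many people had each order. Parts of the protocol were not available for review, and order may be described there.

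**The concern.** In a two-visit within-person comparison, sleep condition and visit number are tied together within each person. Someone who has normal sleep first has restricted sleep at visit 2, and the reverse holds for the other order. If the inflammatory response to the bout differs between a first and a second exposure, for example through familiarity with the test, that difference becomes part of each person's sleep contrast.

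A crossover analysis usually removes this with a period term. For the interaction, the term that matters is visit-by-exercise, which is the same as sequence fitted to each person's contrast. Without it, the shift goes into the error term and, unless the two orders are equally frequent, into the estimate as well. The interaction is the test that answers the stated hypothesis, and it rests on 12 people, so lost precision or a small bias is not easily absorbed.

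**Working it through.** **Inputs from the SAP.** N = 12, alpha 0.05, power 0.80, effect size 0.4; two visits with PRE and POST at each; factors exercise and sleep.

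**Assumptions, not in the documents.** Two-sided testing; size of the visit shift; order split; type of effect size and within-person correlation.

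**1. The plan's own figure.** Take 0.4 as Cohen's f, with noncentrality f²·N·m/(1−ρ), where m is the number of repeated measures and ρ their correlation.
- ρ = 0.5: m = 3 gives N = 12, m = 4 gives 10, and m = 2 gives 15 (power 71% at 12).
- ρ = 0.6 with m = 2 gives 12.
- Reading 0.4 as a paired standardised difference gives 52.

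So 12 can be reached, under choices that the SAP does not state. Nothing below depends on which was used.

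**2. What the interaction tests.** Let D = (POST−PRE) at RS minus (POST−PRE) at NS. The interaction F on 1 and 11 df is the square of the one-sample t on D.
- A constant level shift at visit 2 adds the same amount to PRE and POST, so it drops out of POST−PRE and out of D. A visit main effect alone therefore changes nothing. In five simulated datasets at 7/5, adding one left the interaction t identical (for example 1.7955 both ways, 11 df).
- Adding visit-by-exercise gave exactly the t from regressing D on sequence, on 10 df, in all five.

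**3. Effect of a shift in the response.** Write D = τ + δs + e, with s = +1 for NS first and −1 for RS first, SD(e) = 1, and n1 and n2 the numbers in each order.
- Bias of the planned estimate = δ(n1−n2)/12. At 7/5 with δ = 0.5: 0.5 × 2/12 = 0.083 SD.
- Expected sample variance of D = 1 + δ²[1 − ((n1−n2)/12)²] × 12/11. At 6/6 with δ = 0.5: 1 + 0.25 × 12/11 = 1.27.
- With the term, the estimate is the plain average of the two sequence means, with SE = ½√(1/n1 + 1/n2) = 0.289, 0.293, 0.306, 0.333 at 6/6, 7/5, 8/4, 9/3. The planned SE with no shift is 1/√12 = 0.289.

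**4. Size.** The true effect is set at 0.889 SD, the value that gives the planned test 80% power at δ = 0. Planned-test figures are simulated; power with the term is from the noncentral t on 10 df. Triplets are for δ = 0.25 / 0.5 / 0.8 SD.

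| Split | Bias (SD) | Type I error, planned (%) | Power, planned, shift favours effect (%) | Power, planned, shift opposes effect (%) | Power with term (%) |
|---|---|---|---|---|---|
| 6/6 | 0 | 4.4 / 2.9 / 1.3 | 78 / 72 / 59 | same | 79 |
| 7/5 | 0.04 / 0.08 / 0.13 | 4.6 / 3.6 / 2.2 | 82 / 80 / 74 | 74 / 63 / 44 | 78 |
| 8/4 | 0.08 / 0.17 / 0.27 | 5.2 / 5.5 / 5.5 | 85 / 87 / 86 | 70 / 54 / 30 | 74 |
| 9/3 | 0.13 / 0.25 / 0.40 | 6.2 / 9.2 / 13.1 | 88 / 92 / 94 | 65 / 45 / 20 | 67 |

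With the term, type I error is 5% at every δ and split shown.

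**5. Sleep comparison at a single time point.** A level shift does not cancel from RS−NS at PRE or at POST. With a level shift of 0.5 SD of that difference, type I error without the term is 2.9%, 3.6%, 5.6% and 9.2% at the four splits, against about 5% with sequence. This applies only if simple main effects of sleep means tests at each time point.

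**6. Carryover.** Suppose the restricted night alters the next visit's response by c more than the normal night does. The sequence means of D are then τ + δ (NS first) and τ − δ − c (RS first), and their average is τ − c/2 at every split, including 6/6. Sequence on D cannot separate δ from c.

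**The case against.** The strongest case against is that the planned test is sound in the situations most likely to apply. At 6/6 it is unbiased and its type I error does not exceed 5%. At 7/5 it is still conservative, and the bias at 0.25 SD is 0.04 SD against a standard error of 0.29. Under simple randomisation, averaged over splits, type I error is 5%; a split of 9/3 or worse has probability 15%. No shift is documented. All of this stands, and it is why the point is an improvement rather than a fault.

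Nor does the term always pay. It raises power only when the shift exceeds about 0.15 SD at 6/6, or about 0.35 SD averaged over simple randomisation. At 8/4 with a 0.25 SD shift, power averaged over direction is 77% planned and 74% with the term; at 9/3 it is 77% against 67%. Mean squared error is lower only above √12/(2√(n1·n2)) = 0.29, 0.31 and 0.33 SD at 7/5, 8/4 and 9/3. This also stands. At uneven splits, what the term reliably buys is an estimate free of the visit shift and a 5% error rate at the split actually obtained.

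Three stronger readings are tempting, and the documents do not support them:
- **That visit order was not randomised or counterbalanced.** The available text is silent, and part of the protocol was not available.
- **That any visit effect distorts the interaction.** A constant level shift cancels.
- **That the planned ANOVA inflates false positives.** At 6/6 and 7/5 it does the opposite.

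The objection does not remove one thing: balanced order prevents the bias but not the inflated error variance, and an order description elsewhere would not put a term into the SAP's model.

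**Conclusion.** The point holds as a low-to-moderate-priority improvement. The SAP's model omits the visit-by-exercise term that matches its two-visit design. At a balanced split the consequence is a conservative test: over the assumed shifts of 0.25 to 0.8 SD, power falls by about 1 to 20 points compared with the sequence-adjusted test (79% minus 78% and minus 59%). Bias arises only at uneven splits and may run in either direction.

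These sizes rest on an assumed shift and an illustrative effect of 0.889 SD, neither of which the documents give, and on a split they do not report. The adjusted estimate is unbiased only if there is no unequal carryover between visits. The single-time-point result depends on one reading of an ambiguous phrase. If everyone had the same order, the term cannot be fitted, and the whole shift would sit in the estimate (type I error 12% at 0.25 SD and 35% at 0.5 SD). That case is conditional; nothing in the documents suggests that it occurred.

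**What to change.** Provided both orders were used:
- Compute D for each person, regress it on sequence (NS first +1, RS first −1), and test the intercept on 10 df.
- Treat the NS vs RS sleep comparison the same way, separately at PRE and at POST if that is what simple main effects means, and say which is meant.
- Report how visit order was assigned and the achieved split.
- State that the adjusted estimate assumes no unequal carryover between visits.

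Fix the choice before results are seen. If they have been seen, report the adjusted analysis beside the planned ANOVA as a labelled sensitivity analysis. If only one order was used, state that sleep and visit order cannot be separated.

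Cost: a few lines of SAP, no new data beyond the record of visit order, and one residual df (11 to 10). If there is in fact no visit effect, the term costs about 1 point of power at 6/6, 2 at 7/5, 6 at 8/4 and 13 at 9/3.

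### Could the exercise-by-sleep interaction mistake a higher pre-exercise level for a larger inflammatory response?

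*SAP*

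**What the plan says.** The SAP (Statistical Analysis) describes a two-by-two within-person design. On timing of the samples: "We will collect physiological data from participants at baseline (PRE) and immediately after (POST) a simulated wildland firefighting exercise bout". On the visits: "One visit will occur after a night of normal sleep (NS) while the other visit will occur after a night of restricted sleep (RS"). The main test is stated as: "We will perform a 2-way Repeated Measures ANOVA to assess the interaction between exercise and sleep". It is followed by: "We will additionally test for simple main effects of exercise (PRE vs POST) and sleep (NS vs RS"). The experimental hypothesis is that "sleep restricted will increase the inflammatory response to simulated wildland firefighting exercise", the null is no difference between the sleep conditions in the response, and the threshold is p < 0.05.

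The SAP mentions no raw, log, percentage or fold scale, no baseline adjustment, and no consequence of a PRE difference. The only marker mentioned is in Statistical Power, where the cited study "found an increase in exercise-induced IL-6 in the blood following acute sleep deprivation". The available Protocol text, a recruitment notice, does not bear on the point.

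**The concern.** In most trials a baseline precedes the intervention. Here PRE follows the night of normal or restricted sleep, so restricted sleep may already have moved it. Inflammatory markers such as IL-6 are positive concentrations, and exercise may act on them multiplicatively. In that case a higher PRE alone produces a larger POST minus PRE difference, and an ANOVA on untransformed values would tend to show an interaction in the direction of the experimental hypothesis. A reader could take it as a stronger reaction to exercise when only the starting level had changed. The planned sleep comparison at PRE may not give warning, because 12 people provide little power for a modest shift. And because no scale is written down, it could be chosen after the results are seen.

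**Working it through.** **Inputs.** From the SAP: 12 participants, four cells (PRE and POST under NS and RS), and p < 0.05, taken as two-sided. The SAP's only derived figure is the sample size of 12. Its effect size of 0.4 has no stated metric; read as Cohen's f, 12 results from, for example, two measurements correlated 0.6 or three correlated 0.5. This point does not depend on that figure being right. Assumed, because the documents give none: lognormal values, log SD 0.5 between and 0.3 within persons, and the PRE shifts and fold rises below.

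**Step 1: what the interaction tests.** In this design the interaction F (1 and 11 df) is the square of the paired t on

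D = (POST − PRE under RS) − (POST − PRE under NS).

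Let PRE under NS be a, let RS multiply PRE by k, and let exercise multiply the level by F under both conditions. Then

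D = ka(F − 1) − a(F − 1) = a(k − 1)(F − 1).

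With a = 1, k = 1.25, F = 3: D = 0.25 × 2 = 0.5. NS goes from 1 to 3 (+2.0) and RS from 1.25 to 3.75 (+2.5), both 3-fold. The mechanism is real, but D scales with both factors: k = 1.10, F = 3 gives 0.2, and k = 1.25, F = 1.5 gives 0.125.

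**Step 2: how often the raw test says increased when fold rises are equal** (positive D, two-sided p < 0.05):

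| PRE shift under RS | Fold rise | Raw | Log |
|---|---|---|---|
| none | 3 | 2% | 2.5% |
| +10% | 3 | 5% | 2.5% |
| +25% | 1.2 | 3% | 2.5% |
| +25% | 1.5 | 5% | 2.5% |
| +25% | 3 | 14% | 2.5% |
| +50% | 3 | 36–37% | 2.5% |

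Over between-person log SDs of 0.3 to 0.8 and within-person log SDs of 0.2 to 0.5, the 14% ranges from 5% to 32% and the last raw figure from 11% to 76%. The PRE comparison detects a 25% shift in about 30% of trials at the central SDs. Raw says increased with a non-significant PRE comparison in about 11%.

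**Step 3: is the raw test wrong for absolute change?** No. With equal absolute rises it says increased in 2.0% of trials at PRE +25% and in about 2% at PRE −20%, close to nominal. The log test has the mirror-image property. With equal absolute rises and PRE −20% (1 to 3 against 0.8 to 2.8, folds 3.0 and 3.5), log says increased in 13%. Neither scale is neutral; each answers its own question.

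**Step 4: the price of the obvious remedy**, concluding an increase only if both scales are significant:

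| Truth (NS; RS) | Raw | Both scales |
|---|---|---|
| 1 to 3; 1 to 4.2 (fold ratio 1.4) | 56% | 37% |
| 1 to 3; 1 to 4.8 (fold ratio 1.6) | 83% | 65% |
| 1 to 3; 1.25 to 5.25 (fold ratio 1.4) | 86% | 42% |
| 1 to 3; 1.5 to 5.5 (folds 3.0 and 3.67) | 83% | 18% |

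In every row the response is larger on both scales, and the loss is greatest where PRE does shift. In the first row about 18 people would be needed to recover the raw test's power at 12 (57% against 56%). In that same row, with no PRE shift at all, raw alone is significant in 19% of trials, so a rule attributing such results to the starting level would mislead.

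**The case for a change.** The strongest case for acting is that silence on scale is no protection. PRE is not a neutral baseline, the bias runs towards the stated hypothesis, the word response can be read either way, and the simple effects carry no stated consequence. The SAP is dated "October 2, 2024" and the approval stamp on the recruitment notice reads "Expiration Date 6-15-2022", so the scale might be chosen with data in hand.

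Part of this stands. The SAP does leave the scale and the meaning of response open, and a significant raw interaction alone does not show a larger fold rise. The rest is weaker. Nothing in the SAP implies raw values only, since the same ANOVA runs on logs. The dates do not show whether data existed when the plan was written. With no shift and no effect, taking whichever scale looks better raises the rate of a result in the hypothesised direction only to 3.7%, from 2.2% (raw) or 2.6% (log). With a PRE shift the choice matters more, but the two scales are then estimating different quantities, and both answers can be true. A PRE difference that 12 people cannot establish by significance can still be seen in the cell means and judged from its interval.

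**Conclusion.** No change to the plan is needed. Followed as written on untransformed values, it gives a sound test of whether the absolute rise differs between sleep conditions, which is a legitimate reading of the hypothesis. The 14% and 36–37% figures are false conclusions only if a fold response is meant, which the SAP does not say. They also rest on assumed shifts, a 3-fold rise and assumed variances, and fall to about 5% or less with a 10% shift, or with a 25% shift and a rise of 1.5-fold or less. The documents give no evidence of how far restricted sleep moves PRE here, so the size in this trial is unknown.

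A both-scale requirement would exchange a possible misreading for a certain loss of power in a 12-person study, and could blame a starting-level difference that does not exist. The remaining gap is one of reporting. A competent analyst will name the marker and scale, show PRE and POST for each condition with intervals, and describe the finding as an absolute or a fold increase accordingly. That needs no new test or decision rule.

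### Do simple effects tested at the same p < 0.05 leave the SAP unclear about which test decides the sleep hypothesis?

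*SAP*

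**What the plan says.** The Statistical Analysis section of the SAP describes measurements at PRE and POST on each of two visits, one after normal sleep (NS) and one after restricted sleep (RS), so each participant contributes four cells. The analysis is introduced by its purpose: "We will perform a 2-way Repeated Measures ANOVA to assess the interaction between exercise and sleep". The next sentence adds further tests: "We will additionally test for simple main effects of exercise (PRE vs POST) and sleep (NS vs RS".

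The hypotheses come after that. The experimental one is "Our experimental hypothesis is that sleep restricted will increase the inflammatory response to simulated wildland firefighting exercise". The null is "Our null hypothesis is that there is not difference between NS and RS in the response to simulated wildland firefighting". One threshold closes the section: "Significance will be accepted at $p < 0.05".

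The section does not make the simple effects conditional on the interaction, does not label them secondary or descriptive, and does not say in so many words which test decides the hypothesis. The Protocol text available for review is recruitment material and has no analysis content.

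**The concern.** The hypothesis is about sleep, and one of the added tests also carries a sleep label, NS vs RS. That test addresses a different question. If restricted sleep moves a marker by the same amount at PRE and POST, the response to exercise is unchanged and the stated null is true, yet NS vs RS at POST may well be significant. A report could set that p-value beside the hypothesis and let it pass as support.

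The exercise effects invite a similar slip: finding the PRE to POST change significant under RS but not under NS, and calling the two responses different. With one threshold for everything and no ranking of the tests, the SAP does not expressly forbid either reading. At stake is a false claim that sleep loss amplifies the inflammatory response.

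**Working it through.** **The plan's own figure.** The Statistical Power section reaches 12 participants "using a moderate effect size of 0.4" with "alpha = 0.05 and power = 0.8". It gives no effect-size metric, within-person correlation or number of measurements, so these inputs do not fix N. Reading 0.4 as Cohen's f with two measurements and an assumed correlation of 0.6 gives N = 12 (power 0.805); at correlation 0.5 it gives N = 15 (power 0.714 at 12). So 12 is reachable under plausible assumptions. The present point needs only n = 12, not its derivation.

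**Which test matches the null.** The null is (POST − PRE under RS) − (POST − PRE under NS) = 0. This is the one-degree-of-freedom interaction contrast. Add a sleep shift *s* to both RS cells and an exercise effect *e* to both POST cells. The contrast becomes (s + e − s) − (e − 0) = 0 for any *s* and *e*. NS vs RS at POST becomes (s + e) − e = *s*. The two tests have different targets.

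**Set-up for the rates.** n = 12 (SAP). Two-sided 0.05: the level is from the SAP, the two sides are assumed. Normal data, SD 1 and equal correlation ρ between cells are assumed, with ρ = 0.3, 0.5, 0.7. Each test is a paired t on 11 df, equivalent to the repeated-measures F in a 2×2 within-person design. There were 200,000 simulated trials per setting.

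**No true effects** (the same at all three ρ):

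| What is counted as support | Rate |
|---|---|
| Interaction alone | 5.0% |
| Interaction or NS vs RS at POST | 8.5% |
| Interaction or NS vs RS at PRE or POST | 11.9% |
| Interaction or sleep main effect | 9.8% |

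The last row covers the other reading of the SAP's term for the added tests, which names no level of the other factor. Because those two contrasts are uncorrelated here, 1 − 0.95² = 0.0975 agrees with it closely.

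**Equal sleep shift at PRE and POST, stated null true.** For NS vs RS at POST the standardised effect is dz = s / √(2(1 − ρ)), with noncentrality dz·√12. At s = 0.5 and ρ = 0.5, dz = 0.5 / √1 = 0.5, noncentrality 0.5 × 3.464 = 1.732, power 0.353.

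| Shift *s* | ρ = 0.3 | ρ = 0.5 | ρ = 0.7 |
|---|---|---|---|
| 0.3 SD | 0.127 | 0.158 | 0.232 |
| 0.5 SD | 0.267 | 0.353 | 0.532 |
| 0.8 SD | 0.570 | 0.714 | 0.902 |

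For the sleep main effect dz = s / √(1 − ρ); at s = 0.5 the values are 0.472, 0.608 and 0.821. The interaction stays at 5% throughout.

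**What a gate would cost.** Take a true 1 SD exercise effect, no interaction and ρ = 0.5. PRE vs POST under NS has dz = 1 / √1 = 1 and is significant in 88% of trials. If it could be claimed only after a significant interaction, it could be claimed in about 3.8%.

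**The case for a change.** The strongest case for a change is that a priority left to inference does not bind the report. The SAP has no decision rule, the added tests are unconditional, and one threshold covers them all. The slip is also an easy one. With no interaction and a true 0.6 SD exercise effect (ρ = 0.5), the pattern of a significant RS change beside a non-significant NS change appears in 25.0% of trials. One sentence would close the door at no cost to sample size or data collection. A gate would cut claims about NS vs RS at POST to 2.3 to 2.6% under a 0.5 SD shift.

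Part of this stands: the sentence is absent, and writing it would do no harm. The rest does not carry the point. The 8.5 to 11.9% rates presuppose that either test may support the hypothesis, and the SAP nowhere says so. The 13 to 90% rates across the shift table describe correct detection of a shift that was built in as real. The 25.0% pattern misleads only if an author compares two p-values instead of reading the planned interaction.

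A general gate is a debatable convention, and it would remove nearly all claims about whether the bout raised inflammation at all, a question the misreading of NS vs RS gives no reason to restrict. Choosing one deciding marker or adjusting across markers is a separate matter. Nothing here demonstrates it, and it may be settled in protocol text that was not available.

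**Conclusion.** No change is needed. The purpose given for the ANOVA, the experimental hypothesis and the null all point to the sleep-by-exercise interaction, and the simple effects are introduced as extras. Followed as written, the plan tests its stated null at 5.0% per marker. In this model that figure does not depend on the correlation, or on the size of any exercise effect or equal sleep shift.

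The larger figures need either a decision rule that the SAP does not contain or a mislabelled result in the report. They also rest on assumed normal data, equal variances, equal correlations of 0.3 to 0.7 and assumed shifts of 0.3 to 0.8 SD, none of which the documents supply.

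What remains is an unwritten clarification: that the simple effects are secondary and are not evidence of a changed response. An analyst reading the null would work that way already.
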